TITLE: Randomized Comparative Evaluation of Midline Catheters for Thrombophlebitis

NCT03725293

Approval date: 04/30/2019

Protocol and Statistical Analysis Plan

Randomized Comparative Evaluation of Midline Catheters for thrombophlebitis

Introduction

Establishment and maintenance of intravenous (IV) access are core processes in providing medical care for hospitalized patients. For patients requiring extended duration of therapy, the peripherally inserted central catheter (PICC) Team is often consulted for patient assessment and vascular access device placement at many hospitals. PICCs are central catheters that are placed via peripheral vein under ultrasound guidance and may be used for patients with difficult venous access for long-term central or peripheral infusion therapies as well as central venous pressure monitoring in a critical care setting. Although PICCs provide a great option for some patients, these catheters have known complications including catheter- related bloodstream infection, catheter-related venous thrombosis, malfunction, and high cost. Midline catheters represent a potentially attractive alternative to PICCs for peripheral infusions. These catheters have been utilized since the mid 1980s but fell out of favor in the early 1990s due to reports of acute life threatening hypersensitivity reactions. In the last few years, midlines have made a resurgence in the market and are FDA cleared for use in patients requiring intermediate to longterm infusion therapies. Advances in midline catheters offer the potential for reduced complications. As midlines have increased in popularity and new midlines have been introduced into the market, it is necessary to better understand complication profiles of various midline catheters, as it is likely that all catheters are not created equal. Specifically, the incidence of symptomatic catheter-related thrombosis is of interest. While this complication has been researched extensively for PICCs with an incidence of 1.8 – 8.4%, data on this complication for midlines represents a gap in the literature. One recent publication cited a 4.5% rate of all symptomatic catheter-related venous thrombosis (combined superficial venous thrombosis (SVT) and deep venous thrombosis (DVT)) in patients with midline catheters. Another study found a catheterrelated venous thrombosis rate of 2.5% when limiting measured outcomes to occurrence of DVT. Internal retrospective

data at our institution suggests a rate closer to 12-15% for all symptomatic catheterrelated venous thrombosis (SVT and DVT). Some midline catheters are coated to provide protection against catheter-related venous thrombosis and/or catheterrelated bloodstream infection. The theoretical benefit(s) of these catheters need further validation in human subjects.

Objective

We aim to understand the difference in symptomatic catheter-related upper extremity venous thrombosis (CR-UEVT) comparing the Teleflex Arrowg+ard Blue Advance 4.5 F single lumen midline catheter to the AngioDynamics BioFlo 4 F single lumen midline catheter. Both catheters are inserted using a modified seldinger technique (MST). The AngioDynamics product has Endexo technology with claims of reduced platelet aggregation and favorable thrombus accumulation profile. The Teleflex catheter is a chlorhexidine coated device that claims to be both antithrombogenic and antimicrobial.

Specific Aim 1: To compare incidence of symptomatic CR-UEVT between the AngioDynamics Bioflo midline catheter and the Teleflex Arrowg+ard Blue Advance midline catheter.

For Aim 1, we will measure incidence of all symptomatic CR-UEVT inclusive of superficial thrombophlebitis (SVT) and deep venous thrombosis (DVT) confirmed by upper extremity venous doppler evaluation, to assess whether Arrowg+ard midline catheters offer a reduction in the incidence of symptomatic CR-UEVT.

Specific Aim 2: To compare incidence of catheter-related bloodstream infection between the AngioDynamics BioFlo midline catheter to the Teleflex Arrowg+ard Blue Advance midline catheter.

For Aim 2, we will identify cases of infection per the laboratory confirmed bloodstream infection criteria published by the Center for Disease Control (CDC), to assess whether Arrowg+ard Blue Advanced midline catheters offer reduction in catheter-related bloodstream infection.

Alternatively, for Aim 1 and Aim 2, to further examine the incidence of overall complications in the light of the differing catheter dwell times, catheter days data (including multiple insertions of midline catheters per patient in the study period) will be analyzed.

Specific Aim 3: To compare catheter survival rate data between the AngioDynamics BioFlo midline catheter and the Teleflex Arrowg+ard Blue Advance midline catheter.

For Aim 3, an improved survival of Arrowg+ard Blue Advanced midline catheters will be evaluated by functionality of catheter for intravenous therapy prior to patient discharge. The event is failure of functionality identified during follow-up assessment during hospitalization. Duration of dwell and functional failure of the catheter will be employed to estimate catheter survival.

Study Design

We propose a prospective single-site, parallel, two-arm, randomized investigation to assess catheter-related symptomatic UEVT, catheter-related bloodstream infection, and functionality of two single lumen midline catheters: AngioDynamics BioFlo 4 F and Teleflex Arrowg+ard Blue Advance 4.5 F. The research protocol was approved by the Institutional Review Board of Beaumont Research Institute. Written informed consent will be obtained from all participants.

All inpatients 18 years of age and older that require midline catheter placement by the bedside vascular access team will be eligible participants. Patients will be excluded if: Do not meet inclusion criteria 2. Multiple lumens required 3. Alternative diameter of catheter used 4. If already enrolled once prior 5. Withdraw voluntarily from the study 6. Are receiving oral, intravenous, or subcutaneous treatment dose anticoagulation (prophylaxis with anticoagulant is permissible).

Research staff of Beaumont Health Institute will allocate two midline catheters to eligible participants according to a pre-generated randomized list at a 1:1 ratio in block randomization to AngioDynamics BioFlo or Teleflex Arrowg+ard Blue Advanced midline catheters. Participant enrollment will take place from November 2018 until patient recruitment is complete. Demographic and health-related information will be obtained from electronic medical records during enrolled period at William Beaumont Hospital.

Practitioner Participation/Training

Advanced Practice Providers within the bedside PICC/Midline service at the Royal Oak campus are eligible to place catheters for this study. A cohort of fifteen providers are possible volunteers to be trained to place catheters for this study. Placing catheters for this study is not required and will be carried out on a strictly voluntary basis. All advanced practice providers are credentialed in placing PICCs and midlines by institutional policy and have greater than one year of experience in these procedures. None of the providers have previous experience with the Teleflex Arrowg+ard Blue Advance midline catheter. The clinical team from Teleflex will be expected to develop an educational/training pathway for providers to achieve proficiency prior to subject recruitment. A possible training/credentialing pathway may consist of: 1 hour didactic training followed by phantom training on a vein block and required successful placement of 2-4 catheters on real patients.

Initial Assessment

After written informed consent is obtained, investigators will carry out additional evaluation at the bedside. The research team will capture and save images of vessel depth and vessel diameter in short axis using the Sonosite S1 ultrasound equipment. Ultrasound guidance will be used for the initial assessment and procedure. The high frequency linear array transducer will be used for all procedures. Inserters will evaluate the vessel for valves, thrombosis, trajectory, and collapsibility per routine care. If the vein is appropriate for cannulation, the practitioner will continue with the procedure. Post-cannulation and post securement, functionality is confirmed with blood sampling (10 cc) and flush without resistance.

The research team also will document practitioner details, the vascular access device (VAD) used, the time of VAD placement, number of attempts, need for a rescue inserter, the vein that was cannulated, depth and diameter of the vein, and the indication for VAD placement. An attempt is defined as each time the needle punctures the skin. Data will be collected from the electronic medical record and includes: age, gender, BMI, vital signs, relevant past medical history. Specific medical history of interest includes: 1. VTE 2. Cancer (within past 6 months) 3. Hypercoaguable state 4. Current pregnancy/up to 8 weeks postpartum 5. Major surgery/major trauma within past 4 weeks 6. Estrogen supplementation 7. Long

travel > 6 hours within past 4 weeks 8. Inflammatory Conditions (IBD, SLE) 9. Immobilization >72 hours 10. Other. Indication for catheter placement will also be recorded: 1. DIVA 2. Antibiotics 3. Incompatible Medications 4. Other

Follow-up Assessment

Investigators will perform a follow-up assessment on all catheters within 24 hours of insertion and then daily for the life of the VAD. Generally all follow-up evaluations will occur between 8 am and 10 am. At each follow-up interval, the researcher will document the time of evaluation and assessment of functionality as well as review the patient chart for signs and symptoms of catheter-related bloodstream infection and document the presence of localized site infection. A catheter is functional if the investigator is able to withdraw 3-5 ml of blood or if the VAD flushes without resistance with 5 mL of saline. Even if the line is actively infusing upon evaluation, the investigator will stop the infusion and assess for functionality by drawing blood and flushing. Data specific to blood sampling will be collected daily. If the catheter was identified to have failed during follow-up assessment the date and time of failure and the reason for failure will be documented. If the catheter failed or was removed prior to the follow-up assessment then the VAD failure time and the assessment of failure and reason for line removal will be obtained through chart review. For all failed catheters, re-insertion attempt data will be tracked through the medical record in the nursing section for venous lines and need for reinsertion of the midline or escalation to a PICC, or CVC will be noted. If the patient is discharged prior to the time of follow-up assessment then the time of discharge will be documented and the VAD will be presumed functional until time of discharge unless otherwise noted in the chart.

Some patients may leave the hospital with the midline in place for additional intravenous therapies. If the patient is discharged with the midline, the research team will discuss the infusion plan with the care management team. Patients will also be provided detailed contact information of the Vascular Access Team (standard practice) at the time of hospital discharge in case any questions or complications arise. If the patient develops any concerning signs or symptoms for the venous thromboembolism, the Vascular Access Team will instruct the patient to return to the outpatient clinic for an evaluation with a member of the Vascular Access Team, schedule an urgent appointment with the medical doctor, or check into the Emergency Department for further evaluation. The research team will document imaging results from these encounters. All patients will receive follow-up phone call assessments by the research team. Patient disposition options include: discharge home/residence or to a skilled nursing facility or transfer to another hospital. If the patient is discharged home, infusion and catheter care occurs via home care or at an infusion center. For patients discharged to a skilled nursing facility, catheter care and infusion is managed by nursing staff at these centers. These patients will continue to be followed in the posthospital setting, specifically to assess for the complication of thrombosis. The research staff will follow-up via telephone call with staff managing the infusion within 48-72 hours of discharge and weekly including the last day of therapy to inquire about the VAD site and function of the catheter and document any complications/results to radiographic imaging. Once the rapy is completed and the catheter is removed, the research team will follow up with the patient or designated legally authorized representative/next of kin via phone to inquire about the access site at 30 days post

line removal. All patients will receive the 30 day follow-up phone contact. Patients will specifically be asked if they developed redness, swelling, or pain at the catheter insertion site and had radiographic evaluation for a blood clot or pulmonary embolism. If the patient has a concern, the research team will forward the concern to [name] and [name] for further evaluation per routine.

SVT and DVT rates will be calculated based on upper extremity proven diagnosis of SVT and/or DVT in symptomatic cases. Researchers will review all study subject records in EPIC, the electronic medical records system, and screen enrolled subject data for all upper extremity venous Doppler examinations. Radiology interpretations will be reviewed for findings consistent with CR-UEVT. This review will occur thirty days post patient discharge. Symptoms and rationale for imaging will be documented. This information will be obtained by reviewing the order/provider documentation in EPIC. If the patient is diagnosed with thrombophlebitis, the location of the thrombus will also be documented.

Infection rate will be tracked using confirmed catheter-related blood stream infection data from the surveillance team within the epidemiology department. The team utilizes the CDC definition of laboratory-confirmed blood-stream infection (LCBSI). See Appendix A for LCBSI definitions and pathway for diagnosis.

The medication administration record will be queried for all medications given through each catheter. Vesicants that are generally given via central line or considered caustic to the vessel will be noted in both groups. Number of doses will be recorded. See Appendix B for full list of non-neoplastic vesicants. We will also collect data on patients that received alteplase for occlusion. We will specifically evaluate the relationship of alteplase use and how it relates to catheter-related thrombosis, catheter-related bloodstream infection, and functionality of catheter.

Sample Size and Statistical Analysis

Sample Size: For this randomly allocated, two group experiment, the primary outcome was complication profile in terms of thrombophlebitis. Under Aim 1, based on the preliminary analysis using approximately 13 months of data at William Beaumont Hospital, it suggested the incidence of thrombosis between 12-15% from 1,200 insertions of AngioDynamics BioFlo midline catheters with the diagnosis of symptomatic thrombosis. We established a one-sided Fisher's exact twoproportions test with a type I error $\alpha = 0.05$. In terms of results from previous study [1], sample size was designed to have a power of 80% for detecting a 11% lower in the incidence of thrombosis using Teleflex Arrowg+ard Blue Advanced midline catheters. Based on these criteria, 212 participants will be randomly allocated to 2 study groups (106 per group). This sample size included a 20% buffer to account for potential sample loss. For Aim 3, this sample size has a power of 0.85 to detect a hazard ratio of 1.5 for failure of functionality association with AngioDynamics BioFlo midline catheters, based on a log rank test with a 0.05 one-sided significant level and median time of midline catheter introduction into a vein of 10 days [1]. All above calculations were made using the power software PASS 16.

Statistical Analysis: For Aim 1 and Aim 2, we will use descriptive statistics (frequency, percent) to summarize the incidence of complication profile in terms of thrombosis and infection between these two groups. For Aim 1, a logistic regression model will be built to examine the association between midline catheters and the presence of thrombosis, adjusting for participant characteristics. The odds ratio (OR) associated midline catheters on thrombosis will be estimated. For Aim 2, we will further create cases of bloodstream infection per 1000 catheter-days,

accounting for catheter dwell times. A Poisson regression model will be employed to assess the relative risk (RR) of AngioDynamics BioFlo and Teleflex Arrowg+ard Blue Advanced midline catheters on the presence of infection within any observed catheter dwell time, adjusting for participant characteristics. P-values of less than 0.05 will be considered statistically significant. In addition, for Aim 3, we will create data with the first episode of function failure of catheter on IV treatment. To adjust for any difference in participant characteristics, Cox proportional hazard models will be built. We will evaluate the proportional hazard assumption for each fixed covariate of participant characteristics by the log baseline cumulative hazard plot, Schonfeld residual plot, and the interaction between the covariate and function time of midline catheters. If the assumption is violated, a stratified Cox proportional hazard model will be built. Hazard ratio (HR) of two midline catheters for function failure will be reported.

Site

William Beaumont Hospital, Royal Oak (RO) campus is a 1,100 bed major academic and referral center with Level 1 adult trauma and Level 2 pediatric trauma status. A major teaching facility, Beaumont, Royal Oak has 55 residency and fellowship programs with 454 residents and fellows. Beaumont is the exclusive clinical partner for the Oakland University William Beaumont School of Medicine. The Beaumont Research Institute was established more than 30 year ago at Royal Oak and offers research support services to clinical investigators.

Primary Investigator

I have specialized training in emergency ultrasound and completed fellowship in the field in 2008. Since that time, I have served as Director of Emergency Ultrasound for Emergency Medicine. I also serve as the Medical Director for the hospital vascular access team. Additionally, I have a specific interest in ultrasound-guided vascular access with several peer-reviewed publications and national presentations in this area.

References:

Lisova K et al. The incidence of symptomatic upper limb venous thrombosis associated with midline catheter: Prospective observation. Journal of Vascular Access. 2018. Epub ahead of print.

Klungboonkrong et al. Predictors of deep vein thrombosis associated with midline venous catheter in hospitalized patients: a single-institute experience. Journal of Vascular and Interventional Radiology 2015. 26(2) S146.

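### Aim 3 counts only in-hospital failures but names dwell time, never cut at discharge, as the survival time, so the risk period is undefined for lines that go home

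*Combined protocol and SAP*

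**What the plan says.** Under Objective, Specific Aim 3, the evaluation window is set first: improved survival "will be evaluated by functionality of catheter for intravenous therapy prior to patient discharge". The event follows: "The event is failure of functionality identified during follow-up assessment during hospitalization". The time variable comes last: "Duration of dwell and functional failure of the catheter will be employed to estimate catheter survival". That sentence does not cut dwell at discharge.

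Follow-up Assessment bears on this in four places:

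- Checks are planned for longer than the stay: "Investigators will perform a follow-up assessment on all catheters within 24 hours of insertion and then daily for the life of the VAD".
- For a patient discharged before that day's check, "the time of discharge will be documented and the VAD will be presumed functional until time of discharge unless otherwise noted in the chart".
- Lines can outlast the admission: "Some patients may leave the hospital with the midline in place for additional intravenous therapies".
- Staff managing the infusion are telephoned "within 48-72 hours of discharge and weekly including the last day of therapy", and the calls cover catheter function. The stated purpose of post-hospital follow-up, however, is thrombosis.

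The Statistical Analysis paragraph builds the Aim 3 data set from each catheter's first functional failure and fits Cox models. It states no hospital limit and no censoring rule.

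**The concern.** A survival analysis needs time and events to cover the same period. Here the event stops being countable at discharge, while dwell in its ordinary sense runs to removal. A line that goes home would add days on which no event can be scored. If it then failed at home, its dwell would end and it would be recorded as a non-failure.

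Two analysts could follow the text and produce different survival curves. The reported survival proportions are at stake in both arms. The hazard ratio is also at stake if the arms differ in how often, or for how long, lines go home.

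**Working it through.** **1. The plan's own Aim 3 figure.** Sample Size gives power 0.85 for a hazard ratio of 1.5, one-sided 0.05, 212 participants including a 20% buffer.

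- Events needed (Schoenfeld, 1:1): 4 × (1.645 + 1.036)² / (ln 1.5)² ≈ 175.
- Removing the buffer leaves 212/1.2 ≈ 176 or 212 × 0.8 ≈ 170 lines.
- Power with 176 events: Φ(√176 × 0.4055/2 − 1.645) = Φ(1.04) ≈ 0.85. With 170 events it is 0.84.

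The stated figure therefore reproduces, but only if practically every analysed line is seen to fail. It gives no information on where time is meant to stop.

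**2. Why the time scale matters.** Let the true failure hazard be λ. If time runs to removal but only in-hospital failures count, the recorded hazard on day t is λ × (share of lines at risk on day t that are still in hospital). Whenever some at-risk lines are at home, this is below λ, so estimated survival is too high. If time is censored at discharge, the share is 1 and λ is recovered.

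**3. Inputs for the size.** The documents give neither the stay after insertion nor the share going home, so these are assumptions:

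- Exponential failure with BioFlo median 10 days and hazard ratio 1.5, so the Arrowg+ard median is 15 days. The plan words its 10 days as time in the vein, so using it as time to failure is itself an assumption.
- Gamma-distributed hospital stay, mean 5 days, and further dwell at home, mean 7 days (shape 2 reproduces the figures below). Discharge is independent of failure.
- 20%, 40% or 60% of lines go home, equally in both arms.

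True 14-day survival: BioFlo 0.5^(14/10) = 0.38; Arrowg+ard 0.5^(14/15) = 0.52.

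**4. Results (simulation).**

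| Share going home | BioFlo, dwell to removal with in-hospital events | Arrowg+ard, same rule | BioFlo, censored at discharge |
|---|---|---|---|
| 20% | 0.52 | 0.66 | 0.38 |
| 40% | about 0.59 | 0.70 | 0.38 |
| 60% | 0.63 | 0.73 | 0.38 |

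With longer stays (mean 7 days, then 14 at home), the BioFlo figures under the first rule are about 0.48, 0.53 and 0.57. The overstatement is smaller but remains.

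**5. Hazard ratio.** With discharge the same in both arms, the estimate stays at about 1.5 under either rule, and type I error is about 0.05. With no true difference, and 20% of BioFlo against 40% of Arrowg+ard lines going home, dwell to removal gives a BioFlo hazard ratio of about 1.10 to 1.13, depending on the stays assumed. That wrongly favours Arrowg+ard. Censoring at discharge gives about 1.00 to 1.02.

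**6. Event counts.** Per 212 lines under the 5-plus-7-day assumptions, about 50 failures occur in hospital. Followed to removal, the counts are about 60, 69 and 79 for 20%, 40% and 60% going home.

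**The case against.** The strongest reply is that the plan never says home days are survival time. The aim sets its window before discharge, and Follow-up Assessment records the discharge time and presumes function until then. Read together, dwell may mean in-hospital dwell, with time and event both ending at discharge. That analysis is coherent, and none of the overstatement above arises.

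This largely stands. A reader might infer that the plan prescribes whole-dwell time; the documents do not support that. They leave the point open. The discharge sentence covers only patients who leave before that day's check, and it presumes function without defining censoring. The analysis paragraph is silent.

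Two further points stand:

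- The lower event count follows from any in-hospital endpoint, including the coherent one. It is not evidence of a mismatch.
- Restricting the event to hospital is defensible. Function is judged at the bedside by drawing blood or flushing saline, which a telephone call cannot do, and the calls are mainly about thrombosis. Making failure to removal the main endpoint would be a trade-off.

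**Conclusion.** The concern holds as an undefined and inconsistent risk period. The event is limited to hospitalization, the named time variable is not, and no general rule joins them for lines that leave in place.

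If dwell is taken as insertion to removal, 14-day BioFlo survival is overstated by about 0.14 to 0.25 (0.52 − 0.38 to 0.63 − 0.38) under the shorter assumed stays. The overstatement is about 0.10 to 0.19 (0.48 − 0.38 to 0.57 − 0.38) under the longer ones. These sizes rest on assumed stays, shares going home and exponential failure.

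Two stronger readings go too far. One is that the hazard ratio is biased as planned. It is biased only if going home differs between arms, and the documents give no evidence that it will. The other is that failures learned by telephone are certain to be thrown away. The event definition leaves them out, but the analysis paragraph carries no hospital limit, so their handling is unsettled.

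Aim 3 is not the primary aim. The point should be settled before analysis because the choice changes the reported survival.

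**What to change.** In Specific Aim 3 and in the Statistical Analysis paragraph, replace dwell as the time variable with time from insertion to first functional failure, removal or discharge, whichever is first. Working lines are censored at removal or discharge. Time and event then cover the same period.

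Add a sensitivity analysis that follows both time and events to line removal. It would use the function information from the scheduled post-discharge calls and treat telephone-reported failures as interval-censored between the last contact with a working line and the report.

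The cost is a few sentences, with no new contacts; discharge times are available in the records. The in-hospital version has fewer events. With 176 analysed lines, the failure assumptions above and a fixed stay of T days, expected events are 176 × [(1 − 0.5^(T/10)) + (1 − 0.5^(T/15))]/2. For T = 5, 7, 10 and 14 that is about 44, 58, 77 and 97 events, with power about 0.38, 0.46, 0.55 and 0.64. The Aim 3 power statement should be recomputed from the failures expected under the chosen risk period. In the sensitivity analysis, telephone-reported failures are less exactly dated and do not rest on the bedside function test.

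### Two exclusion items are not confined to the time before allocation, and no rule keeps every randomized patient in the primary analysis

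*Combined protocol and SAP*

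**What the plan says.** Study Design gives one numbered list of reasons for exclusion. Three consecutive items read "Alternative diameter of catheter used 4. If already enrolled once prior 5. Withdraw voluntarily from the study". The item before them, on multiple lumens, is worded as something *required*; the diameter item is worded as something *used*. No item carries a time point.

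The next paragraph says "Research staff of Beaumont Health Institute will allocate two midline catheters to eligible participants according to a pre-generated randomized list". It does not say whether allocation comes before or after the bedside vein assessment. Initial Assessment places that assessment after consent and adds "If the vein is appropriate for cannulation, the practitioner will continue with the procedure", without mentioning allocation.

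The arms differ in diameter. The Objective compares the "Teleflex Arrowg+ard Blue Advance 4.5 F single lumen midline catheter to the AngioDynamics BioFlo 4 F single lumen midline catheter".

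Sample Size and Statistical Analysis allocates 212 participants, 106 per group, and includes a 20% allowance for loss. It plans a logistic model for Aim 1, a Poisson model for Aim 2 and a Cox model for Aim 3. Incidence for Aims 1 and 2 is to be summarized by group. No analysis set is named, and nothing says how a patient who receives another catheter or withdraws is counted.

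**The concern.** An eligibility rule protects randomization only if it is applied before the arm is known. The catheter used is known for certain only at insertion, and leaving a study normally follows joining it. Applied as written, both items can act after allocation.

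The diameter item could act differently by arm. The assigned diameters differ, and Practitioner Participation/Training states that no inserter has used the Teleflex device before, although training is planned before recruitment. If patients dropped from one arm differ in number or thrombosis risk from those dropped from the other, the Aim 1 comparison is between selected groups. The 20% allowance replaces numbers; it does not correct selection. Leaving the rule open also leaves the choice of who counts to be made after outcomes are known.

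**Working it through.** **Setting the passages side by side.**

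1. Diameter item. As a screen, it would mean that the patient needs some other size. As worded, it describes what was placed. It may also mean a size that is neither 4 F nor 4.5 F; a patient given the other study catheter would then be a crossover that the item does not cover.
2. Withdrawal item. Refusing consent is not withdrawal from the study, so a screening reading does not come naturally. Withdrawal after consent but before placement is possible, and the item does not confine itself to that.
3. Analysis section. The groups compared follow from the sentence on random allocation, which points to the allocated arms. That settles which arm a patient belongs to more than it settles whether the patient stays in.
4. Follow-up statements about all catheters, all patients and all records govern data collection, not the analysis set.

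**The plan's own figure.** Inputs: one-sided Fisher exact test, alpha 0.05, 80% power, 12-15% under BioFlo, and 11% lower read as percentage points. At an assumed 14% vs 3%, 88 per group gives power 0.798, and 88 x 1.2 = 105.6, rounded to 106. At 13.5% vs 2.5%, 83 per group suffices, and 83/0.8 = 104. So 106 per group is reproduced closely for a control rate near 14%. I use it below.

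**Illustration of bias (assumed inputs).** True rate 15% in both arms; k of 106 Teleflex patients removed, with thrombosis risk r.

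Rate among those left = (0.15 x 106 - k x r)/(106 - k). Example, k = 5, r = 30%: (15.9 - 1.5)/101 = 14.3%.

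The last column is the chance of a false Teleflex benefit, by exact enumeration of the one-sided Fisher test.

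| k | r | Teleflex rate | False difference (points) | False benefit |
|---|---|---|---|---|
| 0 | - | 15.0% | 0 | 3.5% |
| 2 | 30% | 14.7% | 0.3 | 3.8% |
| 5 | 30% | 14.3% | 0.7 | 4.5% |
| 11 | 30% | 13.3% | 1.7 | 6.6% |
| 2 | 45% | 14.4% | 0.6 | 4.3% |
| 5 | 45% | 13.5% | 1.5 | 6.2% |
| 11 | 45% | 11.5% | 3.5 | 12.7% |

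- At r = 15% there is no bias. With equal losses in both arms there is none either, and the error rate is 3.2-3.4%.
- At r = 5%, losing 11 gives 16.2%, or 1.2 points against Teleflex.
- If BioFlo loses the patients instead, the false-benefit rate is 0.5-3.0% at r = 30% or 45%, and 3.7-5.6% at r = 5%.

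**Unknown outcomes.** Counting k withdrawals as non-events at a true 15% gives 0.15 x (106 - k)/106 = 14.7%, 14.3% or 13.4% for k = 2, 5 or 11, a false gain of 0.3, 0.7 or 1.6 points for that arm. As an invented example, take BioFlo 16/106 and Teleflex 4 events in 101 known plus 5 unknown. The one-sided Fisher p is 0.004 if all 5 are non-events, 0.010 if one is an event, and 0.10 if all are events.

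**Price of keeping off-assignment patients.** Suppose k Teleflex patients get another catheter and have the BioFlo rate. Diluted Teleflex rate = pT x (1 - k/106) + pB x k/106. For 15% vs 4% and k = 5: 0.04 x 101/106 + 0.15 x 5/106 = 4.52%.

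| k | 15% vs 4%: kept / excluded | 12% vs 1%: kept / excluded |
|---|---|---|
| 0 | 83.5% | 95.1% |
| 2 | 81.6% / 82.9% | 93.6% / 95.2% |
| 5 | 78.7% / 82.2% | 91.0% / 95.3% |
| 11 | 72.3% / 80.6% | 84.8% / 95.1% |

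**The case against.** The list is terse and loosely worded, most of its items are plainly screening items, and catheters go to participants already called eligible. On that view, *used* is thin evidence of planned removal after randomization. This stands for the diameter item: a screening reading is plausible. It does not fit the withdrawal item well. Even if both items are screens, the plan still does not say how a later withdrawal or an off-assignment catheter is handled.

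The harm is also hypothetical. Passing 5% in the table takes 5 losses at three times the average risk, or 11 at twice, all from Teleflex. The Fisher test appears only under sample size; the planned analysis is an adjusted logistic model whose covariates and sidedness are not given, and these figures do not describe it. All of this stands.

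Keeping off-assignment patients can take power below 80%: at 15% vs 4%, to 78.7% with 5 and 72.3% with 11. That also stands, and it is the price of the randomized comparison.

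Three stronger readings are tempting and unsupported:

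- A reader might infer that the sponsor intends a per-protocol or as-treated analysis. No passage says so, and the reference to two groups points to the allocated arms.
- A reader might infer that the result will be biased towards Teleflex. No passage shows unequal loss, and the sign depends on which arm loses patients and at what risk.
- Larger error rates follow if patients are assumed to be removed because they had an event. The diameter item would act at insertion, before any thrombosis, so that assumption does not represent it.

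**Conclusion.** The point holds as a fault in the stated rules. Two exclusion items can be applied after allocation, and nothing in the plan says that all randomized patients are kept. The evidence is firmer for withdrawal than for diameter.

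The size and direction of any bias are unknown. The loss counts, the risks of lost patients and the 15% common rate are my assumptions; the error rates illustrate a mechanism and are not evidence that bias will occur. Mild cases stay below the nominal 5%. The change should be made because the gap touches the primary comparison and can be closed before analysis.

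**What to change.** 1. Reword the diameter item as a need, judged before allocation, for a diameter other than those of the two study catheters.
2. Delete withdrawal from the exclusion list.
3. State that the Aim 1 primary analysis includes all randomized participants by allocated arm, whatever catheter was placed, using data up to withdrawal and afterwards where consent allows.
4. Report withdrawals and off-assignment catheters by arm, with a simple sensitivity analysis for unknown outcomes rather than silent counting as non-events. Any as-treated analysis is supportive only.

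If a randomized patient has already been dropped under either item, report this by arm and restore the patient where consent allows.

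Most of the data collection is already planned. The team records "the vascular access device (VAD) used, the time of VAD placement, number of attempts, need for a rescue inserter". Follow-up is broad: "Investigators will perform a follow-up assessment on all catheters within 24 hours of insertion and then daily for the life of the VAD", "All patients will receive the 30 day follow-up phone contact" and "Researchers will review all study subject records in EPIC". The exception is a participant with no catheter placed: daily visits follow catheters and the 30-day call is timed from line removal, so only the record review clearly reaches that patient. How such patients count for a catheter-related outcome is debatable and is a separate choice for the plan to state.

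The cost is wording, some outcome tracing and dilution: about 1-2 power points for 2 off-assignment patients, 4 for 5 and 8-10 for 11, compared with excluding them, on the two assumed rate pairs.
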